7.4.2. SERIOUS ADVERSE EVENT CAPTURE AND REPORTING

ALL serious adverse events, regardless of causality will be reported to the IRB per the JHM IRB reporting requirements. Prompt reporting to the JH SOM IBR of unanticipated problems and SAEs will occur as soon as possible after the PI learns of the event, but in all cases within 10 working days with the exception of death of a JHM participant. In this instance, reporting requirements defined in [Policy 103.6\(b\)\(i\) will be followed.](#)

Serious and expected adverse events will also be reported to FDA as soon as possible and no later than 15 calendar days after the sponsor's initial receipt of the formation. Serious unexpected adverse events will be reported immediately upon learning of the event via phone/fax and within 7 days via MedWatch 3500A.

Also, all SAEs will be immediately reported to our named internal Safety Monitor, [name], MD. [name] is a dermatologist with extensive experience in clinical trials as a PI on more than 10 active IRB protocols. She will provide independent authority to stop the trial, remove any participants from the trial, and otherwise maximally ensure patient safety within the limits of the protocol.

8. STUDY PRODUCT INFORMATION

8.1 AUTOLOGOUS VOLAR FIBROBLASTS

The active component of this therapy is autologous cultured fibroblasts.

PRECLINICAL DATA

The autologous fibroblasts used for this product have not been tested in nonhuman in vivo systems as no suitable model for induction of a volar phenotype exists. Additionally, since this autologous product is derived exclusively from the recipient and will be completely removed at the end of the study, no testing for oncogenic potential will be performed. This approach is supported by the azficel-T clinical safety data in humans.

Other model systems have been discussed to test our therapy prior to moving into humans. However, no ideal animal model exists. The most well-studied human skin equivalent are pigs, but pigs are hooved animals and do not have equivalent volar skin to humans. There are methodological constraints with xenografts that we outline below and we do not believe they represent a useful animal model for testing this therapy.

Xenografts are prepared by taking discarded human skin (eg, from abdominoplasties) and sewing it to the back of an immunosuppressed mouse. The following limitations of the xenograft approach have led to the decision not to pursue this method:

1. Graft preparation obviates applicability

For successful graft “take,” the human skin must be vigorously scraped so that the base of the tissue will allow perfusion of oxygen and blood to the donor human skin. We are interested in injecting our cells into the dermis. A severely damaged dermis that is required for the xenograft model is not applicable to our therapy.

2. Take rate

The take rate of human grafts on mice is extremely low. Thus, an unacceptably large number of human grafts and immunosuppressed mice would be required for the following reasons:

- The size of the grafts would only allow for a single injection and we need at least 2 injections for a comparison between volar and nonvolar fibroblast transplants.
- Replicates are required for validation.
- Discarded human skin for these studies is limited.

3. Infiltrating mouse cells

It has been shown that human grafts are quickly infiltrated with mouse cells, particularly given the preparation to induce the graft to “take.” How these mouse cells might alter our phenotype in unpredictable ways also makes the model less relevant.

4. Wound state

A xenograft is in a chronic “wounded state” given the preparation that is required for the graft to “take.” This state is not equivalent to the scenario into which our cells are being transplanted.

PREPARATION

The fibroblasts are cultured, using standard methodologies, from a small punch biopsy that includes the epidermal and dermal layer taken from a volar (palm or sole) or a nonvolar skin site. During and after in vitro expansion, the fibroblasts are harvested and quality control tests are performed. Greater than 95% of the final suspension is composed of fibroblasts as most of the keratinocytes are removed in the initial stages of processing.

Once the final suspension reaches up to 37.5 million fibroblasts, the cell suspension is cryopreserved in freezing media containing human serum albumin, hetastarch and dimethyl sulfoxide (DMSO) (2.5% human serum albumin, 5% DMSO, 6% hetastarch in sterile saline) at a defined fibroblast cell concentration. Before clinical use, cells are thawed and then injected via an intradermal route into the autologous graft site within 24 hours. For Phase Two’s intermittent dosing, each dose will be frozen separately and thawed the day of injection. The transplant volume will contain no more than 37.5 million cells in 0.75 mL of freezing media.

DOSE SPECIFICS

Dosing of our therapy has also provided challenges. We chose 37 million cells based on a number of considerations, many from our investigations in optimizing hair follicle neogenesis using mouse cells. It is important to note that this value may require some optimization. Lower dosages may be used, up to 37.5 million cells. We also propose to administer multiple doses intermittently over 30 days (see Schema, page 4). In the assay that closely parallels this work, we try to convert tissue identity and create hair follicle structures from single cell slurries of both keratinocytes and fibroblasts. In these efforts, we discovered a continuously enhanced rate of hair follicle creation with a higher amount of fibroblasts and keratinocytes used[11]. In our present effort, we are not injecting keratinocytes but using the native keratinocytes that are present and extend for a much greater area than the injection area. Therefore, to optimize our efforts, we wish to try an adequate number of fibroblasts in a small area to maximize proximity of the fibroblasts to the superiorly oriented epidermis.

We also have conducted in vitro ratio studies and determined that a 4:1 ratio of fibroblasts to keratinocytes was the optimum for KRT9 induction. Given that a keratinocyte is roughly 5 μm in width, a 4-mm punch biopsy would contain approximately 800×800 or 640,000 basal layer keratinocytes and there are roughly 4 layers of cells in the biopsy or 2,880,000 keratinocytes. For a 4-fold increase, this would be a minimum of roughly 7,200,000 fibroblasts. However, we assume that directly thawed fibroblasts will have a 5-fold decreased potency due to thawing and positional effects and, thus, we are interested in injecting around 36 million fibroblasts. Azficel-T injections also use a similar number of cells (18 million). Recent studies testing fibroblasts as therapies for bullous diseases used cells of the same order of magnitude[12].

ADMINISTRATION

The mode of administration and site of inoculation is based on the finding that there is no known cell-to-cell contact between fibroblasts and keratinocytes. In normal skin anatomy, keratinocytes and fibroblasts are separated by the basement membrane zone. Nonetheless, the basis of this therapy is that fibroblasts dictate tissue identity, specifically keratinocyte phenotype. The mechanism of the interaction between fibroblasts and keratinocytes is not known. Therefore, our intent is to put our transplanted autologous fibroblasts in their most native environment in the dermis to promote our desired phenotype. It is for this reason that we are pursuing intradermal injection.

[figure not shown]
9. STATISTICAL METHODS

9.1. SAMPLE SIZE JUSTIFICATION

[figure not shown]
This is a feasibility study and thus sample size is limited due to the experimental nature of the effort. However, if KRT9 increases are as Figure 8 below, then the sample size is justified.

Figure 8: Optical Coherence Technology is non-invasive imaging to monitor for graft site epidermal thickening (images from Drs. [name] and [name] of Johns Hopkins Department of Electrical and Computer Engineering).

Dorsum Hand

Volar Hand

9.2 ANALYSIS PLAN

The first method of analysis will happen during each participant's graft monitoring visits to determine whether they will be one of three "Early Graft Removal" subjects. Three epidermal thickness measurements will be calculated at each monitoring visit for each injection site. We will analyze this data to determine whether volar fibroblasts caused an increase in epidermal thickness. The means of determining whether an increase is statistically significant will be through a t-test statistical analysis of 3 independent readings from the three injection sites (no fibroblasts, non-volar fibroblasts, and volar fibroblasts). We will consider a p value less than 0.05 as significant. For a subject to be designated as an "early graft removal", he/she should have a statistically significantly elevated epidermal thickness in the volar injected site but not the non-volar or vehicle-only injected sites.

For statistical analysis at the conclusion of the study we will average multiple subject's values. We will perform a student's T-test comparing the values of epidermal thickness between at least 3 non-volar fibroblast injections and 3 volar fibroblast injection to determine a p value for a significant difference. We will consider a p value less than 0.05 as significant. We will do the same for KRT9 mRNA values. As more participants complete the study, we will repeat this calculation until our enrollment goal is met.

Power analysis: With a difference of mean assumed to be 2, standard deviation of all samples to be 0.5, alpha 0.06, power of 0.8 then a sample size of 3 participants will be sufficient and our goal will exceed this.

We will perform repetitive interim data analysis as each participant completes the final time point.

We will also calculate average areas of increased epidermal thickness.

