5.2.5 GRAFT MONITORING AND REMOVAL

Dependent upon participant response, as many as six monitoring visits will be conducted to evaluate skin thickness and adverse events (see study Schemas, page 3-4). As per the pre-IND discussion with FDA, persistence of any thickening response is of particular interest. In order to assess this, we will divide the subjects such that there will be 2 groups. The first portion will immediately have graft removal once skin thickness increases in order to assess the molecular features of induction of volar skin, and a 2nd portion of subjects will instead be followed for permanence of effect, and undergo graft removal at the conclusion of 10 months of the study.

The method of dividing the subjects will be as follows. At all monitoring visits all injected sites on all subjects will be measured for epidermal thickness by non-invasive confocal imaging or through the non-invasive measurement of skin induration (as long as those injected sites have not been removed through biopsy). The first three subjects who demonstrate a statistically significant increase of measured epidermal thickness on the volar fibroblast injected side will have their grafts removed during the follow-up visit that the increased thickness determined to be statistically significant.

The means of calculating an increase in epidermal thickness of the volar fibroblast injected site will be through a t-test statistical analysis of 3 sequential readings (within a visit) from the three injection sites (no fibroblasts, non-volar fibroblasts, and volar fibroblasts). For a subject to be designated as an “early graft removal”, he/she should have a statistically significantly elevated epidermal thickness in the volar injected site but not the non-volar or vehicle-only injected sites.

If no subjects show an increase, then all subjects will be followed for epidermal thickness till the end of the study and undergo graft removal at the end of the 10 months. If fewer than 3 subjects are identified before the end of the study to have an increase, then the remainder will undergo graft removal at the end of the study. If more than 3 subjects are identified, then those remaining subjects will be

followed through Visit 8 and undergo graft removal at the end of the 10 month period..

“Early Graft Removal” subjects will skip all remaining graft monitoring visits and instead go directly to suture removal visit.

All subjects will have at least one monitoring visit.

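### The early-removal designation infers a volar-specific effect from 'volar significant, other sites not significant', without naming the comparator or testing volar against non-volar

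*Combined protocol and SAP*

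**What the plan says.** Section 9.2 describes the data for the rule: "Three epidermal thickness measurements will be calculated at each monitoring visit for each injection site". The threshold is "We will consider a p value less than 0.05 as significant". A subject qualifies for early removal if "he/she should have a statistically significantly elevated epidermal thickness in the volar injected site but not the non-volar or vehicle-only injected sites". Section 5.2.5 repeats the criterion ("statistically significantly elevated epidermal thickness in the volar injected site but not the non-volar or vehicle-only injected sites") and describes the data as "3 sequential readings (within a visit) from the three injection sites". It applies the result to "The first three subjects who demonstrate a statistically significant increase of measured epidermal thickness on the volar fibroblast injected side". Those three have their grafts taken early for molecular study, and the others are followed for persistence.

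Neither section says what the reference for 'elevated' is, whether the test is one- or two-sided, or what error rate is intended for the combined condition. Appendix I schedules OCT only from the first monitoring visit onward, so it provides no pre-injection thickness reading.

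Two other places are directly comparative. Secondary objective 1 (Section 2) compares volar sites with both non-volar and vehicle sites. The end-of-study analysis in Section 9.2 is a t-test of volar against non-volar thickness, and the same is planned for KRT9 mRNA.

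**The concern.** The rule compares two significance verdicts rather than two sites. With three readings per site, a non-significant result at the non-volar site is weak evidence that non-volar cells did nothing. Two errors follow.

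- **False volar-only label.** If any fibroblast injection thickens skin, and both cell types do so equally, chance can make one site cross the threshold and the other not.
- **Blocked true response.** If the non-volar site also reaches significance, the flag is forbidden however much thicker the volar site is.

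Both errors remain with a single visit and perfectly matched sites, so they are separate from repeated testing. At stake is the make-up of the early molecular group. Subjects with a generic cell response could enter it as volar-specific responders, and subjects with a clear volar excess could be left out.

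**Working it through.** **The plan's own figure.** Section 9.2 assumes a difference of 2 and SD 0.5 (4 SD), alpha 0.06 and power 0.8, and concludes that 3 participants suffice. A two-sample t-test with n = 3 per group has 4 df and noncentrality 4 × √(3/2) = 4.90. At two-sided 0.06 its power is 96.3%; with n = 2 it is 63.0%. So 3 is the smallest n reaching 80%, and the figure reproduces. It concerns the end-of-study test. The plan gives no operating characteristic for the early-removal rule.

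**Inputs.** From the documents: three readings per site, p<0.05 per test, and the criterion quoted above. Assumed: vehicle as the reference, two-sided tests with significance counted only in the elevated direction, normal independent readings with common SD, one visit, and no site-to-site variation. Shifts are in units of the reading SD.

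**Formulas.** For two sites A and B, t = (mean A − mean B) / √[s²(1/3 + 1/3)], where s² is the pooled variance on 4 df and the critical value is 2.776. Rule as written: volar vs vehicle significant, and non-volar vs vehicle not significant. Direct contrasts: volar vs vehicle significant, and volar vs non-volar significant. Rates are from Monte Carlo with up to 1,000,000 runs per scenario; repeat runs agree to about 0.1 point.

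**Equal thickening at both cell sites (no volar-specific effect)**

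| Common shift | Rule as written | Direct contrasts |
|---|---|---|
| 0 | 2.1% | 0.4% |
| 1 SD | 9.7% | 1.4% |
| 2 SD | 16.6% | 2.2% |
| 2.5 SD | 15.5% | 2.4% |
| 3 SD | 11.7% | 2.4% |
| 4 SD | 3.8% | 2.5% |

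**True volar excess of 4 SD over non-volar (the plan's 2/0.5)**

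| Non-volar effect | Rule as written | Direct contrasts |
|---|---|---|
| 0 | 92% | 91% |
| 2 SD | 54% | 95% |
| 3 SD | 22% | 95% |
| 4 SD | 5% | 95% |

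The last three rows can be checked by hand. With the volar site 6 SD or more above vehicle, its test is almost always significant, so the rule's detection is about 1 minus the power of the non-volar test. From the noncentral t (noncentrality shift × √1.5) that power is 46.3%, 78.3% and 94.8% at 2, 3 and 4 SD, giving 53.7%, 21.7% and 5.2%.

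**Sensitivity to the assumptions**
- *Reference.* If each site is instead compared with three reference readings of its own, the false volar-only rate at an equal 2 SD shift is about 24%.
- *Sidedness.* With one-sided 0.05 tests and vehicle as reference, it is 15.4% as written and 4.7% with direct contrasts at 2 SD.
- *Repeated looks, treated as independent.* At an equal 2 SD shift, 3 to 6 visits give 42% to 66% as written and 6.3% to 12.2% with direct contrasts.
- *Site-to-site SD equal to the reading SD.* At an equal 2 SD shift, 16.7% as written and 9.6% direct; at an equal 4 SD shift, about 9% and 12%. For a 4 SD excess over a 2 SD non-volar effect, detection is 51% as written and 84% direct.
- *Site-to-site SD twice the reading SD.* At equal 2 and 3 SD shifts, 16.7% and 16.0% as written, 18.0% and 20.6% direct.

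**The case against.** **The simulated rule is one reading of the text.** This stands. If vehicle is the reference, the clause that the vehicle site must not be elevated cannot be evaluated, and the calculation omits it. A looser intent, that volar be the one site higher than the other two, is conceivable and would be close to the direct contrasts. The text does not say so, and the problem persists under an own-site reference. The gap in the text is itself part of the point.

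**A 5% error rate is breached.** A reader might infer this, but the documents do not support it. The 0.05 is a threshold for each test, and no rate is stated for the combined rule. Nor is the rule always above 5%: it gives 2.1% with no effect and 3.8% at an equal 4 SD shift. The weakness is that the rate depends on the unknown non-volar response.

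**The trial's efficacy conclusion is undermined.** A reader might infer this too, and it does not follow. The final test already compares volar with non-volar directly, the primary outcome is tolerability (Section 9.2.1), and all subjects are planned to have the three sites excised and analysed (Section 5.2.5.6, Appendix VII). A subject who is not flagged is followed and excised later, not lost.

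**Large non-volar effects are hypothetical.** This is fair. The study hypothesis is volar-specific induction, and with no non-volar effect the two approaches differ by about 1 point. But the non-volar site is there to detect a generic cell effect, and the rule performs worst when such an effect exists.

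**Conclusion.** The point holds as a defect in how the early-removal designation is specified. The comparator is undefined, and a volar-specific effect is inferred from a difference in significance when secondary objective 1 calls for a direct comparison. Under the stated assumptions, roughly 10% to 17% of subjects with equal moderate thickening (1 to 3 SD) would be labelled volar-only at a single visit. A 4 SD volar excess would mostly be missed once the non-volar effect reaches 3 SD. The sizes depend on vehicle as reference, matched sites and SD-unit effects that the documents do not supply; the dependence on the non-volar response does not. The consequence is confined to which three subjects enter the early molecular group, and any effect on the final inference is indirect.

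**What to change.** In Sections 5.2.5 and 9.2, state the comparator and the sidedness, and replace the requirement that the other sites be non-significant. Suggested wording for the statistical designation: epidermal thickness at the volar site is significantly greater than at the non-volar site and significantly greater than at the vehicle site, by direct t-tests on that visit's readings, p<0.05 each. The timing and conduct of graft removal remain for the sponsor to decide.

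The change is one sentence in two places and uses readings already planned. With matched sites, the flag rate falls by about 1 point (92% to 91%) if non-volar cells have no effect. Direct contrasts do not correct repeated looks, and three readings within one site still say nothing about differences between sites. If the site-to-site SD is about twice the reading SD, the false-flag rate is no better than under the present rule; at an equal 4 SD shift it is already slightly worse when the two SDs are equal. The sections should state these limits.

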1 ABSTRACT

Cellular therapy holds great promise in medicine. This proposal will employ autologous fibroblasts in an attempt to help the more than 1.7 million (1 out of every 200) people in the US who have had limb amputations. While improvements in prosthetics have been made, their use is still dramatically limited by pain and skin-breakdown at the stump site. Our long-term goal is to permanently convert the skin at the stump site to **volar type (palmo-plantar)** skin. Volar epidermis is markedly thicker than skin at other locations and **uniquely** expresses Keratin 9 (KRT9) which makes it more friction- and irritant-resistant. We and others have shown that volar fibroblasts have the ability to increase epidermal thickness in 3-D and induce ectopic KRT9 **in non-volar keratinocytes** in both 2-D and 3-D co-cultures. (Given that KRT9 is a suprabasalar keratin, and unique to volar skin, it is an ideal read-out). Therefore our aim is a proof-of-concept demonstration

Hypothesis: Autologous volar fibroblasts have the capacity to induce ectopic volar gene expression such as KRT9 in human subjects. To investigate this, we intend to:

Phase One

1. Inject autologous volar and nonvolar fibroblasts in paired areas of the buttocks, or non-buttocks area. (All non-buttocks areas will exclude genitals, face, or at joints) Perform noninvasive imaging over a maximum period of 6 months to monitor for thickened epidermis/stratum corneum and longevity of effect. Also, if early thickening occurs, then we will remove injected skin area early in ½ of participants for #2.
2. Analyze epidermis by both histology and RT-PCR for features of volar phenotype (KRT9, epidermal thickness, stratum corneum thickness, presence of PAX9^{high}, LMX1b^{low}, EMX2^{low}, SHOX^{low} fibroblasts)

Phase Two

3. Identify optimal methods of delivery that will enhance skin reprogramming and improve conversion of non-volar to volar skin. We propose 2 testing methods with the goal of enhancing volar fibroblast stem cell engraftment: (a) We will investigate the efficacy of multiple, intermittent injections, while holding the total number of injected cells constant. (b) An additional approach is to lightly curette the skin at the injection sites to test if superficial wounding of the epidermis enhances volar fibroblast stem cell engraftment.

If successful, the results of this proposal will be a first to ectopically reprogram human skin identity.

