2 PRIMARY OBJECTIVE

1. To determine the safety and tolerability of the use autologous volar fibroblasts to reprogram non-volar to KRT9-expressing volar epidermis in human participants.

SECONDARY OBJECTIVES

1. To measure non-invasively for epidermal thickening in sites of injection of volar fibroblasts compared to both non-volar fibroblast injection and vehicle only injection
2. To measure for molecular changes in excised injected skin (for example increases in KRT9).
3. To describe persistence of epidermal thickening in sites of injection of volar fibroblasts over time.
4. To evaluate the safety and efficacy of an intermittent, serial dosing regimen of the autologous volar fibroblasts.
5. To evaluate the efficacy of superficial wounding with a curette at the injection sites.

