
If a subject refuses consent for the tattoo marker, but is otherwise willing to complete all other study procedures, then we can use the palpated sacral hiatus, and initiation of the gluteal cleft as 2nd and 3rd universal landmarks. In addition, we will maximize the use of individual landmarks such as nevi, seborrheic keratoses, scars and hemangiomas which are found on human skin. In previous studies that the PI has performed(1), he has used exactly this method for the injection of hyaluronic acid to identify sites months later and had universal success at identifying injection sites. Also, to enhance our ability to identify sites we will not limit injections to one side of the buttocks (or non-buttocks area as above) to enhance the available number of landmarks and ensure proper identification in subsequent visits after the injection. Finally, we will frequently also consult clinical photographs (photographed with rulers) of the injection site taken on the day of injection to optimize our ability to correctly map injection sites.

We will avoid injection into the skin above the ischial tuberosity to minimize discomfort and risks of ulcers

Phase One: Single Dose Injection

After numbing the participant with anesthesia described in Visit 2, two of the sites will be injected with 0.7-0.8 mls of media (5% DMSO, 6% hetastarch and 2.5% human serum albumin) containing 30-40 million autologous fibroblasts into a small area about 3-4mm injection area subepidermally at the level of the epidermis-

dermis junction. The third site will be injected with the same volume of media containing no autologous cells.

Phase Two: Intermittent Dosing Regimen

We do not propose to increase the total number of cells injected, but to inject fewer cells more often. At the PI's discretion, the subject may receive injections of the dosing regimen or injections of 10% DMSO.

Two of the three treated sites will receive cells. A total of 4 injections may maximally occur; the first will always include cells for these sites. The remaining 3 injections may include vehicle and up to 10% DMSO instead of cells administered within 30 days after injection of cellular product.

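### The final analysis in 9.2 does not state within-subject pairing, gives no group-level volar-versus-vehicle thickness contrast, and repeats its 0.05 test as subjects accrue

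*Combined protocol and SAP*

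**What the plan says.** **Design.** The Abstract plans to "Inject autologous volar and nonvolar fibroblasts in paired areas of the buttocks" (or a non-buttocks area). Section 5.2.4, Phase One, gives cells at two sites and adds: "The third site will be injected with the same volume of media containing no autologous cells". Section 5.2.5 lists the three sites as no fibroblasts, non-volar and volar. So each subject supplies all three conditions.

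**Objective.** Secondary objective 1 in section 2 is to measure thickening at volar sites "compared to both non-volar fibroblast injection and vehicle only injection". Secondary objective 2, on molecular changes such as KRT9, names no comparator.

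**Final analysis.** Section 9.2 averages values over subjects and performs a "student's T-test comparing the values of epidermal thickness between at least 3 non-volar fibroblast injections and 3 volar fibroblast injection", significant at p<0.05. It does the same for KRT9 mRNA and repeats the calculation as subjects complete until enrolment is met. The power line in 9.2 assumes a difference of 2, SD 0.5, alpha 0.06 and power 0.8, and concludes that 3 participants suffice.

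**Early removal.** Vehicle readings enter only the per-subject t-test that picks early graft removals (5.2.5 and 9.2). The first three subjects who meet that rule "will have their grafts removed during the follow-up visit that the increased thickness determined to be statistically significant", and early-removal "subjects will skip all remaining graft monitoring visits and instead go directly to suture removal visit".

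**The concern.** Two analysts could both follow 9.2 and report different intervals and p-values, one from a paired and one from a two-group test. With positively correlated sites, the two-group version discards the precision that the within-subject design was built to give.

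Secondary objective 1 is also left half answered. The per-subject removal test classifies one person from three readings per site. It does not estimate the volar-minus-vehicle difference across subjects, although the vehicle site is already there to be measured.

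The repeated 0.05 test is tied to the pairing question. Under correlation the two-group test is conservative, and this partly hides the cost of looking many times. Changing to a paired test without dealing with the repeats would expose that cost.

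**Working it through.** Tests are taken as two-sided; 9.2 does not say. The documents give no site correlation r, so 0.3, 0.5 and 0.7 are assumed.

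**1. The plan's own figure.** Difference 2 and SD 0.5 (9.2) give 2/0.5 = 4 SD. For a two-group t-test with n per group, the noncentrality is 2/(0.5·√(2/n)).
- n=2: power 0.630 at alpha 0.06 and 0.565 at 0.05.
- n=3: noncentrality 4.90; power 0.963 at 0.06 and 0.948 at 0.05.

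So n=3 reproduces, and it stays 3 at alpha 0.05. A paired test with 0.5 as the SD of differences also needs 3 (0.942 at alpha 0.06), so the power line does not show which test was meant.

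**2. Paired power at n=3, alpha 0.05.** The noncentrality is 2/(SD_diff/√3).
- If 0.5 is the SD of differences: 2/(0.5/√3) = 6.93, power 0.908.
- If 0.5 is per site, SD_diff = 0.5·√(2(1−r)). At r=0 this is 0.707, power 0.705. At r=0.25 it is 0.612, power 0.800.

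**3. Interval width at n=20** (Phase One enrolment, section 4.1). Paired half-width over two-group half-width = √(1−r)·t(19)/t(38) = √(1−r)·2.093/2.024. This does not depend on the effect size.

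**4. Size and power at n=20, by simulation.** Power is for an illustrative difference of 0.6 SD, which is not in the documents.

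| r | Interval ratio | Paired interval narrower by | Two-group size | Power, two-group | Power, paired |
|---|---|---|---|---|---|
| 0.3 | 0.865 | 13% | 2.1% | 45% | 58% |
| 0.5 | 0.731 | 27% | 0.8% | 44% | 72% |
| 0.7 | 0.566 | 43% | 0.1% | 43% | 91% |

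At r=0, pairing costs about 2 points of power (44% versus 46%). At the plan's 4 SD effect, power at 20 is about 1 with either test.

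**5. Repeated tests at 0.05, every n from 3 to 20, no true effect.** The chance of at least one significant result is about 23% paired. For the two-group test it is 12%, 7% and 3% at r = 0.3, 0.5 and 0.7.

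**6. Which visit to use.** The simulation had no true effect, 20 subjects, 6 visits and 3 readings per site. Removal occurred when volar exceeded both other sites at p<0.05, for the first three subjects only. False-positive rates of the final paired test, over assumed splits of the variance between site, visit and reading:
- last visit at or before removal: 5.0% to 11.1%, because the triggering visit enters the test;
- first visit: 5.0% to 5.1%;
- final visit, with early-removed subjects lost: 5.2% to 9.4%, biased against volar by 0.01 to 0.14 SD of the difference.

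**7. When early removal can begin.** The schedule tables in Appendices I and II appear to mark early excision only from Day 98, with OCT at that visit. Section 5.2.5 sets no such limit, saying only: "All subjects will have at least one monitoring visit". If the tables govern, every subject reaches Day 98 before any removal, so removal cannot select who is measured then.

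**The case against.** The strongest reply is that the pairing point rests on silence. A paired t-test is also a Student's t-test, the Abstract calls the areas paired, and n=3 fits either version. That stands. A reader might infer that 9.2 prescribes an unpaired test, but the text does not say so. The two-group reading is the natural one because 9.2 compares sets of injections and mentions no within-subject difference.

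A reader might also infer that the two-group test would produce false claims of benefit, or that the sample size is wrong. Neither is supported. A single two-group test is conservative under positive correlation, and n=3 reproduces.

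On vehicle, it is fair to say that objective 1 promises a comparison and not a hypothesis test. An estimate with an interval would meet it, so the contrast should not depend on the main test being significant. It would overstate the gap to say that vehicle is ignored altogether, since it is used in the removal rule, or that a vehicle comparison was promised for KRT9.

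Finally, these are secondary outcomes (9.2.2). The primary outcome is tolerability (9.2.1), and 9.1 calls this a feasibility study. That limits the weight of the point but does not remove it: section 6.3.2 expects the degree and longevity of response to inform later trials, so the precision of the estimate matters.

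**Conclusion.** The point holds as a gap in specification. The missing group-level volar-versus-vehicle thickness contrast follows from the text alone. The unstated pairing is an ambiguity whose cost, if resolved as two-group, is an interval that could be about 13% to 43% narrower at 20 subjects. That range rests on assumed correlations of 0.3 to 0.7. The loss of power matters only for effects well below the plan's 4 SD.

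The repeated 0.05 test belongs to the same point because the conservatism belongs to a single two-group test. With repeats, even the two-group version exceeds 5% at correlations 0.3 and 0.5, and the paired version reaches about 23%. The mismatch between alpha 0.06 and 0.05 is minor. Weight: between minor and advisable.

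**What to change.** In 9.2:

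1. Specify a paired t-test on within-subject differences for thickness and for KRT9, with one value per site. For thickness, use the mean of the three OCT readings.
2. For thickness, take all subjects at one prespecified visit that early removal cannot select, and do not use the triggering visit as the main value. Day 98 would qualify for Phase One if it is confirmed that no graft is removed earlier; section 5.2.5 and the appendix tables must be reconciled on this. Otherwise use the first OCT visit. Report the last available visit as a sensitivity analysis. Say how a missing OCT is handled, since 5.2.5 allows visits without it.
3. Always report the volar-minus-vehicle thickness estimate with its 95% interval. If it is also tested, test it after volar minus non-volar. Testing both unadjusted gives about 9% false positives; the fixed order keeps 5%.
4. Base the reported p-value on one calculation after the last Phase One subject and label earlier repeats descriptive. This must accompany item 1. Analyse Phase Two separately, because its control and cell sites may receive DMSO (5.2.4).
5. Restate the power line at alpha 0.05 and say whether SD 0.5 is per site or of differences.

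**Cost.** No added subjects, visits or tissue. The changes are wording in 9.2, plus reconciling 5.2.5 with the appendices. Pairing has slightly less power if site correlation is near zero. Interim p-values become descriptive. A fixed visit may miss later thickening, especially the first OCT visit, which in Phase One is Day 42, 42 − 30 = 12 days after the nominal injection day.
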